9.2.9.1 Pharmacokinetic Blood Sampling

The plasma concentration/time curves of CBD and its major metabolites will be assessed at Visits 3 and 10 for patients weighing more than 20 kg. Where appropriate, blood samples will be taken as follows:

- One sample pre-dose (i.e., prior to administration of IMP).
- One sample between 2 and 3 hours post-dose.
- One sample between 4 and 6 hours post-dose.
- One sample between 8 and 10 hours post-dose (patients 18 years and above only).

There must be a minimum period of at least two hours between each of the blood sampling time points. In the event of an AE that, in the opinion of the investigator, is related to a concomitant AED, additional blood samples may be collected.

For patients who undergo PK blood sampling, the patient/caregiver will record all meal times and the types of meals consumed by the patient during all PK testing days (Visits 3 and 10).

Analysis of all pharmacokinetic samples will be conducted at a central clinical laboratory. Sample volume requirements and processing procedures will also be detailed in a separate laboratory manual.

Study Code: GWEP1521
EudraCT Number: 2015-002154-12
Protocol V8 23Apr19

The patient/caregiver must be advised that it may not be safe for them to undertake further blood tests within one month of any study-related blood draws and to inform the investigator if they suffered any blood loss during the one-month period leading up to a planned blood draw.

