Cognitive and Behavioral Function:

- Changes in Vineland Adaptive Behavior Scales, Second Edition (Vineland-II).
- Changes in Wechsler Scales (pre-school, primary, children, adult).
- Changes in Achenbach Child Behavior Checklist (CBCL) and Adult Behavior Checklist (ABCL).

Autistic Features:

- Change in Social Communication Questionnaire (SCQ) score.

Study Code: GWEP1521
EudraCT Number: 2015-002154-12
Protocol V8 23Apr19

PK (Blinded Phase Only):

- The plasma concentrations will be summarized by time window for CBD and its major metabolites following single and multiple doses of GWP42003-P. Where data allows, the area under the plasma concentration curve (AUC_{0-t}) from time zero to the last measurable time-point will be calculated.
- Plasma concentrations of concomitant AEDs before and after treatment with GWP42003-P, where available.

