13.6.4 Pharmacokinetics

Plasma concentrations for CBD and its major metabolites, following single and multiple doses of GWP42003-P will be summarized by treatment group. Estimates of PK parameters will also be summarized using the appropriate statistics.

Where available, plasma concentrations of concomitant AEDs will be summarized.

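### AUC0-t ends at the last sample, scheduled at 4–6 h under age 18 and 8–10 h in adults, so the default summary by arm pools areas over different intervals

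*Protocol*

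**What the plan says.** The AUC sentence stands in the Synopsis (Exploratory Endpoints, PK), in Section 4.1.2 and in Section 13.6.3. Where the data permit, AUC0-t is computed "from time zero to the last measurable time-point will be calculated". No fixed upper limit is given.

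Section 9.2.9.1 (and the Synopsis, Procedures, PK) sets the sampling. The curves "will be assessed at Visits 3 and 10 for patients weighing more than 20 kg". The draws are:

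- "One sample pre-dose (i.e., prior to administration of IMP"), all PK patients
- "One sample between 2 and 3 hours post-dose", all PK patients
- "One sample between 4 and 6 hours post-dose", all PK patients
- "One sample between 8 and 10 hours post-dose (patients 18 years and above only")

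It adds that "There must be a minimum period of at least two hours between each of the blood sampling time points".

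Section 6.1 admits ages 1 to 65, so both schedules occur in one PK set.

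Section 13.6.4 says that concentrations "will be summarized by treatment group. Estimates of PK parameters will also be summarized using the appropriate statistics". The first half of that quotation, on treatment group, ends the sentence about concentrations. The second half is a separate sentence about PK parameters and names no grouping. For AUC the grouping comes from Section 13.4, which tabulates blinded-phase data by randomized arm unless something else is specified.

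**The concern.** The integration limit and the sampling schedule are both fixed in the protocol, and they do not fit together. Read literally, an adult and a 12-year-old with identical concentration curves get different AUC0-t values, because the adult's area covers about four more hours. Nothing in the text puts the two on a common footing.

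An exploratory objective is the PK of cannabidiol and its metabolites after single and multiple doses, and AUC is the only exposure parameter named. A mean or median AUC over both ages has no single meaning: it depends on the share of adults among those sampled, and its spread includes a part that comes only from the schedule. In a trial spanning ages 1 to 65, readers will also tend to compare children with adults, and on this definition adults look more exposed even when they are not.

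**Working it through.** The protocol states no AUC, half-life, absorption rate or PK sample size, so there is no planned figure to reproduce. The check holds the concentration curve identical in adult and minor and lets only the scheduled samples differ.

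**1. Constant concentration C (no PK assumption beyond flatness).** The area is C × t, so the ratio is the ratio of the end times.

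| Minor's last sample | Adult's last sample | Ratio |
|---|---|---|
| 5 h (mid-window) | 9 h (mid-window) | 9/5 = 1.80 |
| 6 h | 8 h | 8/6 = 1.33 |
| 4 h | 10 h | 10/4 = 2.50 |

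**2. Assumed one-compartment oral profiles.** With absorption rate ka and elimination rate ke = ln 2 / half-life, C(t) ∝ ka/(ka − ke) × (e^(−ke·t) − e^(−ka·t)). The area is the linear trapezoid over the scheduled times. Assumed, not in the documents: ka from 0.3 to 2 per h, half-life from 2 to 60 h, zero pre-dose concentration at Visit 3, and 12-hourly steady state at Visit 10 (the protocol says twice daily).

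One case in full, Visit 3, ka = 1 per h, half-life 8 h (ke = 0.0866):

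- C(2.5) = 0.792, C(5) = 0.703, C(9) = 0.502
- AUC0-5 = 2.5 × (0 + 0.792)/2 + 2.5 × (0.792 + 0.703)/2 = 0.990 + 1.868 = 2.858
- AUC0-9 = 2.858 + 4 × (0.703 + 0.502)/2 = 2.858 + 2.409 = 5.267
- Ratio = 5.267/2.858 = 1.84

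Over the whole grid:

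| Visit | Mid-window (2.5, 5, 9 h) | Shared third sample, times moved to window edges |
|---|---|---|
| 3 (first dose) | 1.35–2.45 | about 1.1–4.0 |
| 10 (steady state) | 1.35–1.81 | about 1.1–2.5 |

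The ratio exceeds 1 in every one of these cases.

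**3. Effect on a pooled summary.** Let a share p of the sampled patients in an arm be adults, all with the same constant C and mid-window samples. The pooled mean is (5 + 4p)·C and the standard deviation produced by the schedule alone is 4·√(p(1 − p))·C. The share p is not in the documents:

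- p = 0.10: mean 5.4C, SD 1.20C, coefficient of variation 22%
- p = 0.25: mean 6C, SD 1.73C, 29%
- p = 0.50: mean 7C, SD 2C, 29%
- p = 0.75: mean 8C, SD 1.73C, 22%

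**4. Draw times within the windows.** At constant concentration, a last sample at 6 h rather than 4 h gives 6/4 = 1.5 times the area. This source of variation exists within the under-18 group too.

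**The case against.** Four objections have weight.

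- **Pooling is not stated outright.** A reader might infer that Section 13.6.4 itself orders AUC to be summarized by treatment group. It does not: those words govern concentrations, and the pooling of AUC follows only from the Section 13.4 default, which yields to any other specification. The SAP was not at hand and may set an age split or a common interval. This stands as a limit on the claim. It does not remove the point, because the protocol itself fixes the integration limit and the age-dependent schedule.
- **The size depends on assumptions.** A reader might take a single range, such as 1.5- to 2.4-fold, as a property of this trial. The documents give no profile to support that, and at Visit 10 the mid-window ratio stays at or below about 1.8 on the grid used. Only the time ratios in step 1 come straight from the schedule, and they assume flat concentrations.
- **Dose arms and visits are largely protected.** A reader might infer a biased comparison of 25 with 50 mg/kg/day, or a spurious change between visits. Section 7.2 stratifies randomization by age, with 18–65 as a stratum, so the adult share should be similar across arms. Each patient has the same windows at both visits, and under Table 8.1.2-1 the planned dose rises from 5 mg/kg/day at Visit 3 to 25 or 50 by Visit 10, a 5- to 10-fold change that already dominates any raw contrast.
- **The reach is small.** The endpoint is exploratory and descriptive, AUC is conditional on the data permitting it, and no adult-versus-child PK comparison is planned. Concentrations by time window are unaffected, since the 8–10 h window holds adults only.

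**Conclusion.** The point holds as a badly fixed definition of minor severity. As written, AUC0-t covers 4–6 h under 18 and 8–10 h in adults, and no provision in the protocol makes the two comparable before the default summary by arm. For identical curves the adult area is about 1.8 times larger at mid-window if concentrations are flat (1.33 to 2.5 at the window edges). On the assumed profiles the mid-window ratio is about 1.35–2.45 at Visit 3 and 1.35–1.8 at Visit 10.

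What suffers is the spread and meaning of the pooled exploratory AUC, and any adult-versus-child reading of it. The documents do not support extending this to the dose-arm contrast or to PK results generally, and no efficacy conclusion depends on it.

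**What to change.** Amend the AUC sentence in the Synopsis and in Sections 4.1.2 and 13.6.3, and the summary sentence in Section 13.6.4, in one of two ways:

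1. **Common partial AUC.** Use an interval that every fully sampled patient covers, for example 0–4 h with linear interpolation between the 2–3 h and 4–6 h samples, for all pooled summaries. Report the longer AUC for adults only, on its own line.
2. **Age split.** Keep AUC0-t and summarize it separately for under 18 and 18+.

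With either, the scheduled adult-versus-minor mismatch goes: for the same profile and the same sample times the ratio is 1.0 under option 1, and option 2 no longer pools the two groups.

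The cost is wording only, with no new samples. Option 1 drops the adults' late sample from the pooled summary, and option 2 gives smaller groups. Variation in draw times remains under option 2. Option 1 reduces it without removing it: at constant concentration the 6 h versus 4 h discrepancy falls from 1.5 to 1.0. On assumed first-dose profiles with ka 0.3–1.0 per h and half-life 3–24 h, sampling at 0, 3 and 6 h rather than 0, 2 and 4 h changes the area by +26% to +84% for AUC0-t, but by −20% to −6% for the interpolated 0–4 h area. For very fast profiles (ka 2 per h, half-life 2 h) interpolation does worse, about −31% against +2%, so actual draw times should be reported with either option.

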13.6.4 Pharmacokinetics

Plasma concentrations for CBD and its major metabolites, following single and multiple doses of GWP42003-P will be summarized by treatment group. Estimates of PK parameters will also be summarized using the appropriate statistics.

Where available, plasma concentrations of concomitant AEDs will be summarized.

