2.3 Exploratory

Blinded Phase:

- To evaluate the effect of GWP42003-P on TSC-associated neuropsychiatric disorders (TAND), including cognitive and behavioral function and autistic features compared with placebo.
- To determine the pharmacokinetics (PK) of CBD, and its major metabolites following single and multiple doses of GWP42003-P.
- To evaluate the effects of GWP42003-P on plasma concentrations of concomitant antiepileptic drugs (AEDs), if applicable.

Open-label Extension:

- To evaluate the long term effect of GWP42003-P on TAND, including cognitive and behavioral function and autistic features.

Study Code: GWEP1521
EudraCT Number: 2015-002154-12
Protocol V8 23Apr19

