8.2 Concomitant Therapy

It is theoretically possible that GWP42003-P may modify the metabolism of other drugs (including AEDs) administered concurrently and there remains the possibility of pharmacological interactions between GWP42003-P and other concurrently administered drugs. Doses of any concomitant AEDs must have been stable for at least four weeks prior to screening and must remain stable throughout the blinded study period. If during the blinded or OLE phase plasma concentrations of concomitant AEDs are found to be altered following administration of IMP, or if there are side-effects suspected of being related to an elevation in the concomitant AED concentration, the investigator must contact the GW medical monitor to discuss best management. Decisions should be based on clinical symptoms and not plasma levels of AEDs. Further information on drug interactions can be found in the IB⁵¹.

Concomitant AED dose reductions are permitted on clinical grounds (e.g., due to AEs or transaminase elevations **not meeting** withdrawal criteria specified in [Section 10](#) and [Section 12.8](#)) following discussion with the GW medical monitor.

Study Code: GWEP1521
EudraCT Number: 2015-002154-12
Protocol V8 23Apr19

Additional new AEDs (including oral mTOR inhibitors) are not allowed to be added during the randomized phase of the trial but may be considered on a case-by-case basis for the OLE phase in accordance with local licensing and after consultation with the GW medical monitor.

The use of rescue medication is allowed when necessary. Any medication, other than the IMP, taken during the study must be recorded on the Case Report Form (CRF).

Any non-pharmacological therapies (e.g., ketogenic diet, vagus nerve stimulation) must also be stable up to four weeks prior to screening and throughout the duration of the study.

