9.2.9.2 Determination of Plasma Concentrations of Concomitant Antiepileptic Drugs

Plasma concentrations of concomitant AEDs will be assessed at Visits 3, 5, 7, 9 and 10/ the Withdrawal visit (if possible) during the blinded phase and at Visits B2, B3, B4 and all subsequent Assessment Visits during the OLE. Samples will be collected for all patients provided that the risk/benefit outcome is favorable in the investigator's opinion. At each visit, blood samples will be taken prior to administration of IMP. Patients will be instructed to record the dosing time of their concomitant AEDs in the diary.

Additional blood samples may be taken for AED monitoring if there is a suspicion of changes in AED levels, with the aim to keep the AED plasma levels within the patient's therapeutic level. AED doses should be adjusted, as appropriate, following discussion with the GW medical monitor in order to maintain stable AED plasma concentrations.

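### Sections 9.2.9.2 and 8.2 of the Protocol conflict on adjusting AED doses to plasma levels, and any such adjustment attenuates the exploratory AED-concentration summary toward no interaction

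*Protocol*

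**What the plan says.** **Objective, endpoint and analysis (Protocol)**
- Section 2.3: "To evaluate the effects of GWP42003-P on plasma concentrations of concomitant antiepileptic drugs (AEDs), if applicable".
- Section 13.6.3, exploratory PK endpoints: "Plasma concentrations of concomitant AEDs before and after treatment with GWP42003-P, where available".
- Section 13.6.4: "Where available, plasma concentrations of concomitant AEDs will be summarized".
- Section 13.4 makes randomized treatment group the default for blinded-phase tables.

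**Management of AED doses (Protocol)**
- Section 9.2.9.2: "AED doses should be adjusted, as appropriate, following discussion with the GW medical monitor in order to maintain stable AED plasma concentrations". The same section says "Additional blood samples may be taken for AED monitoring if there is a suspicion of changes in AED levels", with the aim of holding levels in the patient's therapeutic range.
- Section 8.2: AED doses "must remain stable throughout the blinded study period". When levels are altered in either phase, the investigator contacts the medical monitor, and "Decisions should be based on clinical symptoms and not plasma levels of AEDs". It also says "Concomitant AED dose reductions are permitted on clinical grounds".
- Section 9.2.5 asks for stable AED doses, and section 8.3 lists dosage changes of epilepsy medication as prohibited.
- Section 10 foresees a reduction of the IMP or of a hepatotoxic AED for transaminase elevations that fall short of withdrawal.

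**Sampling and cut-off (Protocol)**
- AED levels in the blinded phase are drawn at Visit 3 before the first dose, then at Visits 5, 7, 9 and 10 (section 9.2.9.2).
- Section 13.6.1 ends the evaluable period the day before a relevant AED change. Its other two limits are worded for IVRS and CRF efficacy data, and section 13.6.4 does not refer to it.

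**The concern.** Section 9.2.9.2 tells sites to hold constant the quantity by which the study is to detect an interaction. A level drawn after an AED dose change reflects the new AED dose as well as GWP42003-P. If the change was made because the level had moved, the later sample understates the movement. Patients with the largest shifts are the likeliest to be adjusted, so the before/after summary leans toward no interaction.

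The contradiction with section 8.2 adds a second problem. A site that follows 9.2.9.2 and a site that follows 8.2 would produce levels with different meanings, and the summary would mix them. A SAP can choose how to tabulate the samples, but it cannot settle which rule sites were meant to follow.

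**Working it through.** **1. The two rules side by side**

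| Question | Section 8.2 | Section 9.2.9.2 |
|---|---|---|
| May AED doses change in the blinded phase? | Must stay stable; reductions allowed on clinical grounds after discussion with the medical monitor | Should be adjusted, as appropriate, after the same discussion |
| What is the basis of the decision? | Symptoms, not levels | Keeping levels stable |
| Phases covered | Stable doses: blinded phase. Basis of decision: blinded and OLE | Sampling in both phases; no phase limit on the adjustment sentence |

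The second row cannot be resolved by assigning the sections to different phases, because section 8.2 applies its rule on the basis of decisions to both. The list of changes in Protocol Amendment 5 shows section 8.2 rewritten to its present form and shows no change to 9.2.9.2, which may be how the two came apart.

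**2. Effect on the summary**

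The Protocol gives no figure for this endpoint, so there is nothing to reproduce. The following is an illustration; all three inputs are assumptions:
- R: the after/before concentration ratio at constant AED dose, taken as the same for every affected patient.
- f: the share of affected patients whose AED dose is adjusted before the later sample.
- c: the share of the log change that the adjustment reverses (c = 1 is full correction).

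Mean log ratio = (1 − f) × ln R + f × (1 − c) × ln R = (1 − f × c) × ln R.

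Observed geometric mean ratio = R^(1 − f × c).

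With full correction (c = 1):

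| R | f = 10% | f = 25% | f = 50% | f = 100% |
|---|---|---|---|---|
| 1.5 | 1.44 | 1.36 | 1.22 | 1.00 |
| 2.0 | 1.87 | 1.68 | 1.41 | 1.00 |
| 3.0 | 2.69 | 2.28 | 1.73 | 1.00 |

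For example, 2^(1 − 0.25) = 1.68. With half correction (c = 0.5), a true doubling shows as 1.93, 1.83, 1.68 and 1.41 for the same four values of f.

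**3. Would restricting to samples before any AED change cure it?**

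Not reliably. Suppose half the patients have R = 1 and half R = 3. The true geometric mean ratio is (1 × 3)^(1/2) = 1.73. If every patient with R = 3 has the AED dose changed before Visit 5, the first on-treatment AED sample, the restricted summary contains only patients with R = 1 and shows 1.00. The restriction removes the patients with the largest shifts.

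**4. Dose-normalised levels**

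If concentration is proportional to AED dose, the level divided by the current daily AED dose has an expected after/before ratio of R, whatever f and c are. The data are already collected: AED changes go into the CRF (section 9.2.5) and AED use into the daily paper diary (section 9.2.11).

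**The case against.** The strongest objection is that sample selection and dose-normalisation for a descriptive exploratory table are usually left to the SAP, which is not shown, and that section 13.6.4 states nothing false. This stands in part: silence on dose-normalisation alone would not be a finding. But the adjustment rule, the endpoint defined as a measured level, and the conflict between 8.2 and 9.2.9.2 are all Protocol text.

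It can also be said that section 8.2 restrains adjustment by level, and that 9.2.9.2 itself says only as appropriate and after discussion. That is fair, and it means the share of patients adjusted could be small.

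A reader might infer more than the documents support:
- **That all samples are pooled.** Section 13.4 defaults to randomized group, and nothing says that samples before and after an AED change are combined. The Protocol only specifies no separation of them.
- **That an interaction would be cancelled out.** This needs every affected patient to be adjusted and every adjustment to be complete. Attenuation is what can be supported.
- **That only the active arms are affected.** Attenuation of an interaction arises where there is one, but section 8.2 allows AED reductions on clinical grounds in any arm.
- **That labelling or interaction advice rests on this table.** No section says so; for interactions, section 8.2 refers to the Investigator's Brochure.

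**Conclusion.** Sections 8.2 and 9.2.9.2 contradict each other on whether AED doses are to be changed in response to plasma levels, and must be reconciled. This review takes no position on which rule should govern. To the extent that doses are changed in response to levels, the measured before/after summary is attenuated toward no interaction, and the Protocol specifies nothing that separates or corrects the affected samples.

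The size is unknown. The range of 1.87 to 1.41 for a true doubling rests on an assumed 10% to 50% of affected patients being fully corrected and on one common true ratio. The direction assumes that adjustments work against the observed change. The objective is exploratory, and the summary is descriptive with no test or power attached, so the severity is minor.

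**What to change.** 1. Reconcile sections 8.2 and 9.2.9.2 so that sites have one statement on whether, and on what basis, AED doses may change in each phase. The content is for the sponsor's clinical team.
2. In section 13.6.4, summarise by AED, randomized group and visit both the measured level and the dose-normalised concentration (level divided by current daily dose of that AED) for all samples.
3. Show samples before and after the first change in that AED's dose separately, and tabulate AED dose changes by arm.
4. Treat a summary limited to samples before any change as supportive only, because it can drop the patients with the largest shifts.

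Cost: a wording change, one derived variable and a few extra tables, with no new visits or blood draws. Dose-normalisation assumes roughly proportional AED kinetics, which the Protocol does not state; showing the measured levels alongside lets the reader judge.

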13.6.5 Safety

In the presentation of safety data for the blinded phase, data from the two cohorts of placebo patients (25 mg/kg/day and 50 mg/kg/day dosing volumes) will be presented separately and pooled together. This will allow the possibility to explore any effects of the volume of IMP on safety endpoints.

